9.7 Interim Analyses

No interim analyses will be performed.

9.8 Analysis of Safety Data

Descriptive and tabular analyses of the safety data will be performed based on information from all patients having received at least one transfusion. The study will use the NCI CTCAE v4.0.

9.9 Sample Size Rationale

Given that the experimental design is a 2-treatment 2-period 2-sequence crossover, the number of patients enrolled should be an even number; thus, we will enroll N=16 participants and assign them depending upon RBC unit availability for the first exchange transfusion. The primary considerations in choosing N = 16 enrollees as the target sample size included:

- the anticipated frequency of missing data,
- o anticipated levels of precision of estimators,
- o anticipated levels of power of hypothesis tests,
- o costs and time requirements.

Our assessment of anticipated levels of precision and power focused on Aim 1. Those considerations were informed by a previous study⁷⁹ of 24-hour posttransfusion RBC recovery (PTR %), in which the point-estimates and interval-estimates of the population standard deviation (σ) of PTR were as follows:

Previous study ⁷⁹		Estimates of the mean		Estim	Estimates of σ	
	n	estimate	95%CI	estimate	95%CI	
Normal donors	27	85.3%	[84.1, 86.5]	3.2%	[2.5, 4.4]%	
G6PD-deficient	10	78.5%	[73.2, 83.7]	8.4%	[5.8, 15.3]%	

Precision of estimators of the means in Aim 1. The above table suggests conjectures about the magnitudes of standard errors (SE) of the means that can be anticipated for the proposed crossover study:

Proposed crossover study (n=16)	SE of the mean = SD/($16^{1/2}$)		
	Expected	Plausible Range	
A: units from normal donors	0.8%	[0.6, 1.1]%	
B : units from G6PD-deficient donors	2.1%	[1.5, 3.8]%	
A vs B : mean difference (if ρ =0.5) ¹	1.8%	[1.3, 3.4]%	
A vs B : mean difference (if ρ =0.0) ²	2.2%	[1.6, 4.0]%	
1 The SEs in the 3rd row correspond to	SD = 7.3% and [5.0.	13.61%.	

The SEs in the 3rd row correspond to SD = 7.3% and [5.0, 13.6]%.

2 The SEs in the 4th row correspond to SD = 9.0% and [6.3,15.9]%.

This table of SEs suggests that precision will be adequate for estimation of regimen-specific mean PTR% in the proposed crossover study of n=16 patients. For example, the width of the 95%Cl for the regimen-**A** mean is expected to be $\pm 1.6\%$ (i.e., 1.96 standard errors). The width of the 95%Cl for the regimen-**B** mean is

expected to be $\pm 4.2\%$, approximately. The third row in this table conservatively assumes that the correlation between a pair of PTR values is "moderate" (ρ =0.5). The fourth row's assumption (ρ =0) is ultra-conservative.

Power of a test procedure in Aim 1. We consider a test of the null hypothesis that "The PTR(%) mean difference between regimens **A** and **B** is exactly zero in the target population of patients." If we assume that

- (1) the mean absolute PTR difference is Δ =10% in the target population of current and future SCD patients,
- (2) the SD of the differences in the target population is σ_{diff} =7.3% (or plausibly 5.0% $\leq \sigma_{\text{diff}} \leq 13.6\%$)
- (3) the correlation between paired PTR measures (for **A** and **B**) is $\rho = 0.50$ in the target population, and

(4) the sample size is n = 16 participants with complete data,

then the chance of drawing a sample of patients that would yield a p-value smaller than $\alpha = 0.05$ is 99%; this power level drops to 78% if $\sigma_{diff} = 13.6\%$. If $\Delta = 5\%$ and $\sigma_{diff} = 7.3\%$ in the target population, then the power level would be 72%; this power level drops to 28% if $\sigma_{diff} = 13.6\%$.

While the planned analysis strategy for Aim 1 will rely on a longitudinal linear mixed-effects model that accounts for period effects, the above estimates of anticipated precision and power are based on the assumptions of a simplistic model for paired 24hr PTR (%) outcomes. The resulting estimates are thus approximate but provide reasonable guidance about precision and power for the proposed study.

In summary, our sample size analysis suggests that a target enrollment of N=16 participants is adequate to provide satisfactory levels of precision for the estimators of mean PTR(%) and is expected to easily provide a high level of power for a test of difference when the treatment effect is near 10% or larger --even if a few participants do not have complete data. The estimates suggest that a smaller sample size would not provide adequate precision for key estimators (i.e., the confidence intervals would be too wide).

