	For Aim 2c, the outcomes of interest are the metabolomic profile from blood samples obtained longitudinally.						
	For Aim 2d, pain scores , occurrence of infection , and antibiotic use will be obtained via a daily 4-week diary for evaluation of pain on an ordinal scale (0,1,2,,10), occurrence of infection symptoms, and use of antibiotics (type, duration, dose).						

Study Design	For this Phase II, single-blind, longitudinal controlled trial, the experimental design is a two-treatment, two-period, two-sequence cross-over design. The two treatment regimens are (A) infusion of G6PD-deficient donor units, and (B) infusion of G6PD-normal donor units. Due to the scarcity of G6PD-deficient units in the donor pool, we will exchange units that are available at the time of scheduled study exchange (likely normal units) and not utilize a randomization scheme. Each 4-week study exchange period will be separated from the second study exchange by a 4-month washout interval. During the washout period, we will look for suitable units (likely G6PD-deficient) for the second study exchange.
Sample	N = 16 eligible patients will be enrolled
Participation Time	Each enrollee's participation will last at least 6 months
Enrollment Time	Recruitment and enrollment of the participants will require 4 years

SCHEMA

Protocol: Single blind, randomized, crossover study

Figure 1: Study Schema: We will compare two treatment regimens via is a two-treatment, two-period, two-sequence cross-over design: CO(2,2,2). The two treatment regimens are (**A**) infusion of G6PD-deficient donor units, and (**B**) infusion of G6PD-normal donor units. The two sequences (**AB** and **BA**) will be assigned to the N=16 enrollees by RBC unit availability at the time of the first study exchange transfusion.

The two 4-week periods will be separated by a 4-month washout interval. The outcome measures of interest are 24-hour ⁵¹CR-labeled PTR of RBCs, and Hemoglobin A evaluated before and 4 weeks after infusion.

Period/ Procedure					Fo		Follow	-up visits			
Study Day/Visit Day	24-72 hrs pre- infusio n	Pre- transfusio n	5,7.5,10,12.5,15, 30 min post infusion	1 hr post transfusion/ infusion (+/-15 min)	24hr post infusion (+/- 3 hours)	48 hr post infusio n (+/- 3 hours)	72hr post infusio n (+/- 3 hours)	1week post infusio n (+/- 1 day)	2week post infusio n (+/- 2 days)	3 week post infusio n (+/- 2 days)	4 week post infusio n (+/- 2 days)
Informed consent	х										

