2 SPECIFIC AIMS

2.1 Primary Objective (Aim 1)

Aim 1. Evaluate the effects of blood from a donor with G6PD-deficiency on 24-hour post-transfusion recovery (PTR) as measured by Chromium 51 (⁵¹CR).

We hypothesize that, in contrast to the decreased PTR we found in healthy adult recipients, adults with SCD have a greater decrease in PTR when receiving older, stored RBCs from G6PD-deficient donors, as compared to G6PD-normal donors. We anticipate that the mean difference (i.e., the treatment effect) is larger than we observed in our previous study of healthy controls (6.8%).

The Aim 1 investigation will be considered a success if the confidence interval estimate for the treatment effect (i.e., the mean difference in PTR between G6PD-deficient donors and G6PD-normal donors) in SCD patients is not too wide. With an n = 16 participants with complete data, with a hypothesized difference in PTR of 10%, the chance of drawing a sample of patients that would yield a p-value smaller than α = 0.05 is 99%.

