9.2 Study Design

For this Phase II, single-blind, controlled trial, the experimental design is a two-treatment, two-period, twosequence cross-over design: CO(2,2,2). The two treatment regimens are

Regimen **A** transfusion of one G6PD-deficient donor units stored 15-25 days

Regimen **B** transfusion of one G6PD-normal donor units stored 15-25 days The two sequences of treatment are **AB** and **BA**. The two 4-week periods will be separated by a 4-month washout interval. We believe the 4-month washout interval will be adequate to prevent carryover effects from period1 into period2 because RBCs normally only survive 120 days (4 months) at their maximum normal survival.

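### Section 9.9 reverses the regimen letters, uses 1.96 to 2 standard errors where t with 15 df applies, and gives no half-width for the treatment difference that decides Aim 1

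*Combined protocol and SAP*

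**What the plan says.** **Regimen letters.** The Study Design row of the Protocol Summary gives the regimens as "A) infusion of G6PD-deficient donor units, and (B) infusion of G6PD-normal donor units". Section 9.2 agrees: its Regimen A is "transfusion of one G6PD-deficient donor units stored 15-25 days". In the standard-error table of section 9.9 the first row is "A: units from normal donors", and row B is the G6PD-deficient units. The sentences after the table carry the reversed letters on without naming the donor type: ±1.6% for the regimen-A mean and about ±4.2% for the regimen-B mean.

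**Multiplier.** The ±1.6% is explained as "i.e., 1.96 standard errors".

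**What the half-widths cover.** They are given for the two regimen means only. For the A versus B difference, 9.9 prints standard errors: 1.8% (range 1.3 to 3.4) at correlation 0.5, and 2.2% (range 1.6 to 4.0) at correlation 0.

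**How Aim 1 is judged.** Under section 2.1, Aim 1 succeeds if the confidence interval for the mean PTR difference "in SCD patients is not too wide". The closing summary of 9.9 defends the sample size on the ground that "a smaller sample size would not provide adequate precision for key estimators".

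**The concern.** Section 9.6 treats point and interval estimates as the study's most important results, and section 2.1 makes an interval width the success criterion for Aim 1. The precision statement in 9.9 is therefore a main part of the case for N=16. It has three defects.

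- Read with the definitions in 9.2, the letter-only sentences credit the tight interval to the deficient regimen, whose planning SD is 8.4%, and the wide one to the normal regimen, whose SD is 3.2%.
- The half-widths use a normal multiplier although the SD will be estimated from 16 patients. The powers in the same section use t.
- The reader is told how precisely each regimen mean will be estimated, but not how wide the interval for the difference will be, and the difference is what section 2.1 judges.

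**Working it through.** **Inputs, all from section 9.9.** SD for normal donors 3.2% (2.5 to 4.4). SD for G6PD-deficient donors 8.4% (5.8 to 15.3). n = 16, so SE = SD/4. SD of the paired difference 7.3% (5.0 to 13.6) at correlation 0.5, and 9.0% (6.3 to 15.9) at correlation 0. Half-widths are in percentage points of PTR.

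**1. The plan's SDs and SEs reproduce.** With SD_diff = sqrt(a² + b² − 2ρab):

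- ρ = 0.5: sqrt(3.2² + 8.4² − 3.2×8.4) = sqrt(53.92) = 7.34, SE 1.84
- ρ = 0: sqrt(3.2² + 8.4²) = sqrt(80.80) = 8.99, SE 2.25

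The ends of the SD ranges give 5.04 and 13.64 at ρ = 0.5, and 6.32 and 15.92 at ρ = 0. All agree with the footnotes to the table.

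**2. The plan's half-widths reproduce, with a normal multiplier.**

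- Normal units: 1.96 × 0.8 = 1.57, stated as 1.6
- Deficient units: 1.96 × 2.1 = 4.12, which rounds to 4.1; 2 × 2.1 = 4.20, the stated 4.2

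So the first is 1.96 SE (2 SE would also round to 1.6) and the second is 2 SE.

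**3. The plan's powers reproduce with t and not with the normal approximation.** The test is taken as a two-sided paired test at 0.05; the plan does not state the sidedness, but two-sided reproduces its figures.

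| Effect | SD of difference | Stated | t, 15 df | Normal |
|---|---|---|---|---|
| 10% | 7.3 | 99% | 99.9% | >99.9% |
| 10% | 13.6 | 78% | 78.5% | 83.7% |
| 5% | 7.3 | 72% | 72.6% | 78.2% |
| 5% | 13.6 | 28% | 28.0% | 31.2% |

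The first row does not discriminate. The last three do, including the one introduced by "this power level drops to 78% if" the larger SD: they fit t and miss the normal values by 3 to 6 points. Section 9.9 therefore uses t for power and a normal multiplier for interval width.

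**4. Half-widths with t.** t(0.975, 15) = 2.131.

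- Normal mean: 2.131 × 3.2/4 = 1.71, so ±1.7 (stated 1.6)
- Deficient mean: 2.131 × 8.4/4 = 4.48, so ±4.5 (stated 4.2)

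**5. The missing half-width for the difference,** from the printed SDs:

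| Correlation | SD (range) | Half-width (range) |
|---|---|---|
| 0.5 | 7.3 (5.0 to 13.6) | 3.89, so ±3.9 (±2.7 to ±7.2) |
| 0 | 9.0 (6.3 to 15.9) | 4.80, so ±4.8 (±3.4 to ±8.5) |

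**6. Sensitivity to the degrees of freedom.** If a period effect takes one degree of freedom (14 df, t = 2.145), the point values are 1.72, 4.50, 3.91 and 4.83. They round to the same ±1.7, ±4.5, ±3.9 and ±4.8.

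**7. The letters.** Section 9.2 and the Protocol Summary have A deficient and B normal; the 9.9 table and text have A normal and B deficient. The values sit with the right donor type: 3.2/4 = 0.8 is on the row naming normal donors, and 8.4/4 = 2.1 on the row naming deficient donors. Only the letters are reversed.

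**The case against.** The case on the other side is good on size. Every stated figure reproduces. The plan discloses its multiplier, marks the ±4.2% as approximate, and describes the precision and power work as resting on a simplified paired model. The t correction is 0.1 and 0.3 points, small beside the stated SE range of 1.5 to 3.8 for deficient units. The table rows name the donor type beside the letter, so a careful reader can decode the two sentences that follow. The SEs of the difference are printed for both correlations, so the half-width is one multiplication away. Printing it would not settle section 2.1 by itself, because no number is attached to the success criterion.

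Most of that stands, and it is why the point is minor. It does not remove the point. The caveat about a simplified model concerns paired outcomes against the planned mixed model; it does not explain two reference distributions within one section. The letters do contradict 9.2. And the half-width for the difference is the figure a reader needs to give the success criterion any content.

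Three stronger readings are tempting, and the documents do not support them.

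- *A reader might infer that the precision was computed for the wrong regimen.* The SEs match the SDs of the donor types named in their rows, and neither the SE of the difference nor the power depends on which regimen is called A.
- *A reader might infer that the trial's own 95% intervals will be too narrow.* The 1.96 multiplier is a planning figure. Section 9.6 plans a mixed-effects model with an F-test for Aim 1 and nowhere says that final intervals will be 1.96 SE.
- *A reader might infer that N=16 is too small or the power overstated.* The stated powers already use t and reproduce.

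**Conclusion.** The point holds as a minor one. The regimen letters in 9.9 contradict 9.2 and the Protocol Summary. The two stated half-widths are slightly too narrow for n=16: ±1.7% against ±1.6% for normal units, and ±4.5% against ±4.2% for deficient units. The half-width for the treatment difference is absent; it is ±3.9% at correlation 0.5 or ±4.8% at correlation 0, and reaches ±7.2% or ±8.5% at the upper ends of the plan's SD ranges.

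These values rest on the plan's own planning SDs, 16 patients with complete data in both periods, and a simple paired analysis with 15 df. The correlation is an assumption, so both of the plan's cases are shown.

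**What to change.** In section 9.9:

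1. Change the letters in the table and text so that A is G6PD-deficient and B is G6PD-normal, as in section 9.2. Name the donor type in the two half-width sentences.
2. Restate the 95% half-widths with t on 15 df: ±1.7% for normal units and ±4.5% for deficient units.
3. Add the 95% half-width for the treatment difference: ±3.9% at correlation 0.5 (±2.7 to ±7.2 for SD 5.0 to 13.6) and ±4.8% at correlation 0 (±3.4 to ±8.5 for SD 6.3 to 15.9). Refer to it from section 2.1 as the figure against which the Aim 1 width criterion is to be read.

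The cost is a few text and table edits. The half-widths for the means grow by 0.1 and 0.3 points. Nothing changes in the SDs, SEs, powers, N=16 or the planned analysis.

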10 PLANS TO ENSURE DATA QUALITY

Database System for Data Capture

Data will be collected and entered into a web-based data management system (RedCAP). The lead coordinator will routinely verify that all data entry fields are entered. Verifications are question-by-question checks that give immediate feedback to help catch data entry errors, form completion errors, and out-of-range values. Reports of outstanding edits, generated upon completion of data entry, will enable continuous cleaning of data.

Confidentiality

Each subject is assigned a unique number to assure confidentiality. Any publication or presentation will refer to subjects by this number and not by name. The medical records department, affiliated with the institution where the subject receives medical care, maintains all original inpatient and outpatient chart documents. Subject research files will be kept in a locked room or locked cabinet.

Data Management Plans

The Principal Investigator will serve as the trial coordinator for this study. The PI or designee will monitor timely entry of data into the study database. Access to all source documentation maintained by the lead coordinator, including correspondence and source data, will be available for monitoring and audit purposes.

11 DATA AND SAFETY MONITORING PLAN (DSMP)

Disposition of Participants

- 1) The subject completes the 2 chromium infusions and associated lab draws
- 2) The subject decides to withdraw from the study
- 3) The subject moves away, dies, or is lost to follow-up
- 4) Subjects may be removed from the study, or treatment stopped by the Investigator for any of the following reasons:
 - Occurrence of CTCAE Criteria of grade 3 or higher that are deemed attributable to the chromium infusion per the opinion of the PI
 - PI decides to withdraw the subject due to noncompliance
 - Withdrawal by the PI or subject because of transfusion side effects or complications

Data and Safety Management Overview

The UNC Safety Monitoring Committee (SMC) and the UNC Institutional Review Board (IRB) will approve protocol-specific DSM plans. A local, investigator-initiated trial will be required to be continuously monitored by the principal investigator of the study with annual safety and progress reports submitted to the SMC.

11.1 Study Team

The study team minimally consists of the principal investigator, the clinical research coordinator, regulatory specialist and the study biostatistician. While subjects are on treatment, the principal investigator will meet regularly with the research coordinator and the study biostatistician to review study status. This review will include but not be limited to reportable SAEs and update of the ongoing study summary that describes study progress in terms of the study schema. The appropriateness of further subject enrollment and the specific intervention for a next subject enrollment is addressed.

11.2 Quality Assurance

The UNC Clinical Trials Office provides ongoing quality assurance audits.

11.3 SMC

UNC places the highest priority on ensuring the safety of patients participating in clinical trials. Every clinical trial conducted at UNC includes a plan for safety and data monitoring.

The SMC is an independent board appointed by the PI composed of three members. The principal role of the SMC is to regularly monitor the data from the clinical trial, review and assess the performance of its operations, and make recommendations, as appropriate, to the PI and IRB.

The PI will be notified within 24 hours of learning of an event when a serious adverse event possibly, probably or definitely related to red cell transfusion or an event resulting in death (regardless of attribution) is reported. The PI will review the event as soon as the materials are available. The PI may request additional information regarding the event and may request the subject's treatment arm assignment. Following the review, the PI will sign a log summarizing the event.

The SMC chairperson will receive information on all serious adverse events possibly, probably, or definitely related to red cell transfusion and all events resulting in death (regardless of attribution) within 7 days of the PI becoming aware of the event. The SMC chair will have expertise in benign hematology and transfusion medicine, will review the serious adverse event materials, and determine if the information is complete.

The SMC members will meet annually via teleconference. All adverse events will be reviewed during the call, and the group will determine if additional SMC review is required, and make recommendations about the study.

This study will be reviewed by a Safety Monitoring Committee (SMC). A summary of the SMC activities are as follows:

- Review the clinical trial for data integrity and safety.
- Review all unexpected grade 3, and all grade 4, and 5 adverse events, as well as any others requiring expedited reporting as defined in this protocol. (Grades 4 and 5 events must be reported to the SMC within five calendar days of study staff's knowledge.)
- Submit a summary of any recommendations related to study conduct.
- Terminate the study if deemed unsafe for patients.

A copy of the UNC Data and Safety Monitoring Plan and membership roster will be maintained in the study research file and updated as membership changes. The committee will review reports from the study principal investigator annually (or more frequently if needed) and provide recommendations on trial continuation, suspension or termination as necessary.

For this pilot study, the site-PI will appoint three members to a Safety Monitoring Committee (SMC). These will be investigators from institutions with expertise in transfusion medicine, SCD, and biostatistics. They will be charged with monitoring the accruing data to confirm that the patients in the trial are being cared for safely.

The SMC will meet at least once per year, and will be responsible for:

- 1) reviewing and analyzing the progress of the study
- 2) approving amendments to the trial protocol
- 3) monitoring the safety of the study treatments and diagnostic procedures
- 4) ensuring data quality
- 5) reviewing interim analyses and recommending early stopping or continuation of the trial
- 6) reviewing recruitment and event rates.

The data safety monitoring plan will ensure that the site is in compliance with Federal regulations, Good Clinical Practice and Good Manufacturing Practice Guidelines, as applicable.

The SMC will meet at least once per year, either in-person or via teleconference. Prior to the meeting, the site-PI will provide the SMC with:

- Accrual totals
- Adverse event log reports for each study subject
- Serious adverse event reports for each study subject
- Study compliance issues
- The SMC will also be provided each subject's study arm assignment by the primary site biostatistician.

The SMC will determine:

- All-cause mortality
- Number, type, and severity of serious adverse events
- Number of subjects in each treatment arm with at least one clinically documented pain crisis leading to an ED or hospital admission

- Unexpected adverse events and unanticipated problems
- Serious infection or pain admissions

For the sessions, results will be overall and by RBC unit group.

Any available SMC letters will be submitted to the IRB of record as required.

